3.4 Study Centres

The study will be conducted at the Singapore Baby and Child Clinic(SBCC) Gleneagles Medical Centre in Singapore. Communication with study personnel, including asking questions or reporting of AEs or SAEs will be conducted over the telephone or email messaging as appropriate.

3.5 Duration of the study per subject

The duration of the study will be approximately 2 weeks for each subject from their primary caregiver(s)/legally acceptable representative(s) signing the informed consent) until completion of end of study questionnaire

For the subpopulation with Cocoon Cam the duration of the study will be approximately 3 weeks for each subject from their primary caregiver(s)/legally acceptable representative(s) signing the informed consent) until completion of end of study questionnaire.

4 SUBJECTS

4.1 Study population

20 infants aged 2 to 12 months of age. Consideration would be made to recruit 10 infants with > 1 hr crying every day and primary caregiver having concern about infant's crying pattern.

4.2 Inclusion criteria

1. Infants aged 2 to 12 months.
2. Primary caregiver should have reliable access to the internet and a reliable device such as a computer, tablet or smartphone to access the COOL mobile app and able to view the LENA data and complete questionnaires.
3. Primary caregiver should be adequately comfortable in English to read the content in the COOL mobile app and complete questionnaires.
4. Primary caregiver takes care of the child more than 50% of the time

4.3 Exclusion criteria

1. Primary caregiver who is not adequately comfortable in English language to read the content in the COOL mobile app and complete questionnaires.
2. Incapability of the primary caregiver to access COOL mobile app using a reliable device with internet.

4.4 Subject recruitment

Subjects will be approached for participation in the study if they are eligible and interested to take part by their treating physician. To facilitate recruitment, advertisements, posters, social media and/or referral sites may be used.

4.5 Instructions and restrictions during the study

There are no restrictions during the study. The primary caregiver will be instructed to perform the study procedures as a part of her regular routine chores.

4.6 Subject discontinuation during the study

4.6.1 Criteria for subject discontinuation

Infants may be withdrawn from the study at any time (i.e. from any further study procedure, but not from analysis) for the following circumstances:

- 1) At the primary caregiver's request.
- 2) If, in the PI's opinion, continuation in the study would be detrimental to the infant's well-being.
- 3) Poor compliance, as defined at the discretion of the PI (e.g.: a situation in which the primary caregiver does not adhere to the study procedures).

4.6.2 Procedures in case of subject discontinuation

Discontinued subjects must be reported to the study monitor. For any subject who discontinues participation before completion of the study protocol, the Investigator must complete the CRF up to the last conducted assessment, the early termination visit pages and the study summary. Whenever feasible, the following information should be documented on the early termination visit pages in the CRF:

- Early termination date
- Reasons for early termination
 - Adverse Event
 - Withdrawn informed consent
 - Lost to follow-up
 - Protocol violation
 - Other (to be specified)
- Date and time of study product's last use
- Physical examination (if appropriate)
- Follow-up evaluation/end of study

All data collected until the moment of subject discontinuation will be retained and further used by Danone Nutricia Research. No new data will be collected after the moment of subject discontinuation, except for follow-up of safety data. For subjects who discontinue the study due to the occurrence of (serious) adverse events potentially related to the study procedure, appropriate follow-up will take place until the adverse event has abated, or until a stable situation has been reached, with findings being recorded in the CRF. Alternative medical care of the discontinued subject is to be arranged by the Investigator if necessary.

The study coordinator must make every effort to contact primary caregiver of infants lost to follow-up. Attempts to contact the primary caregiver of infants must be documented in the site record (e.g.: dates and times of attempted telephone/email contact).

Infants whose study participation is terminated prematurely for any of the above listed criteria will be replaced at the PI's discretion.

5 STUDY PARAMETERS

5.1 Primary outcome parameter

The rating by the primary caregivers on the use and relevance of the cry and fuss clock generated from the LENA recorder data and the rating by the primary caregiver on the level of engagement due to the content on the COOL mobile app.

5.2 Secondary outcome parameter

The rating by the HCPs on the use and relevance of data provided by the LENA recorder in their general practice.

5.3 Exploratory outcome parameter(s)

- Total crying and fussing time captured by the LENA recorder
- Crying and fussing time perceived by the primary caregiver
- Vital parameters like heart rate, sleep recorded by the Fitbit used by the primary caregiver during crying and fussing events registered by LENA
- Comments and feedback provided by the primary caregiver on the LENA recorder and the COOL mobile app
- Comments and feedback provided by the HCP on the LENA recorder and the data provided
- Sleep time recorded by the Cocoon Cam
- Crying time recorded by the Cocoon Cam
- Crying start and end time recorded by the primary caregiver in the COOL app
- Sleep start and end time recorded by the primary caregiver in the COOL app
- Comments and feedback provided by the primary caregiver and HCP on the Cocoon Cam and the activity log for infant cry and sleep including push notifications in the Cocoon Cam app
- Usage data from the Cocoon Cam app

5.4 Safety parameters

Incidence, frequency, seriousness, severity and relatedness of AEs related to the study product

5.5 Other parameters

5.5.1 Demographics, subject and family characteristics

Parameters for describing demographics and subject characteristics in this study are:

- Sex [male/female]
- Date of birth of the infant
- Race and Ethnicity of the infant
- Birth characteristics of the infant (Gestational period, mode of delivery)
- Relevant medical history (including pre-existing conditions)
- Relevant prior medication given to the infant due to medical history
- Relevant medication given to the infant due to any adverse event related to the study product
- Feeding characteristics of the infant
- Household characteristics of the infant (Order of the child in the household, number of siblings, subject and sibling's child care)
- Primary caregiver characteristics (Date of birth, mobile usage, highest level of education, occupational status)

5.5.2 Crying pattern history and primary caregiver experience

Infant's crying pattern and primary caregiver's experience due to subject's crying and/or fussing for last 7 days before enrolment will be collected through primary caregiver reported questionnaires on the mobile app at enrolment.

The primary caregiver's feedback on the use and relevance of the data provided by the LENA recorder and their feedback on the level of engagement due to the content on the COOL mobile app will be collected through self-reported questionnaires at day 7 and 14.

A daily questionnaire on the average total minutes the subject cried/fussed and the time of the day the subject cried or fussed most based on primary caregiver's perception will be collected for 14 days from enrolment through primary caregiver reported questionnaires on the mobile app.

If the primary caregiver consents for the use of Cocoon Cam, the actual crying, fussing and sleeping time will be recorded by the primary caregiver through daily diary. In addition, the primary caregiver will need to complete a questionnaire on the usability of the Cocoon Cam at Day 7 and 14.

At the end of the study post clinic visit, a questionnaire to understand if the information from the LENA recorder helped to objectively articulate the discussion with the doctor will be collected through primary caregiver reported questionnaires on the mobile app. If the primary caregiver use Cocoon Cam, a feedback from the doctor on the usability of Cocoon Cam will be collected.

5.5.3 *HCP Feedback*

At the end of the study post clinic visit, HCP will complete a questionnaire to provide feedback on the usability and relevance of the cry and fuss data generated by the LENA recorder in their daily practice.

5.5.4 *Data from Fitbit*

Vital parameters like heart rate and sleep pattern from Fitbit of the primary caregiver.

5.5.5 *Data from Cocoon Cam*

Sleep, Crying data captured by Cocoon cam and the usage data for the Cocoon Cam app .

5.5.6 *Protocol compliance*

Parameters for assessing protocol compliance in this study are:

- Adherence in answering to the daily questionnaire
- Use of the LENA recorder
- Adherence to the visit window

6 STUDY PROCEDURES AND ASSESSMENTS

6.1 Procedures per visit

Screening period:

At screening visit, after parent(s) / guardian(s) of potential subjects and/or legal representatives have been informed about

the study, they will be requested to sign the informed consent form (ICF) prior to start of the study. After successful signing of the informed consent, the investigator will assess the eligibility of the subjects. If the subject meets all the inclusion and none of the exclusion criteria, the primary caregiver will complete a detailed questionnaire on subject's demographics, family characteristics, household characteristics and feeding characteristics. The primary caregiver will also complete a questionnaire about primary caregiver's characteristics. The primary caregiver will be provided the LENA recorder kit. If the primary caregiver consents for use of Fitbit, the primary caregiver will be provided with the Fitbit. The primary caregiver will be needed to complete a training period in order to verify a subject's primary caregiver's ability to properly connect, operate and upload data using the LENA recorders and uploader. As part of the training period, the primary caregiver will do 1-2 hours of recording using the LENA recorder and successfully upload the data into the LENA cloud server through internet within 2 days of screening. The study coordinator would provide support if the primary caregiver faces any challenges and have any questions. Please note that if the primary caregiver is unable to perform all of the technical prerequisites (after troubleshooting assistance is provided), they will not be able to take part in the trial and will be dismissed as a screen failure, as well as, having to return the LENA recorders and uploader and the Fitbit(if provided). Once the study coordinator verifies that the upload is successful, the training and feasibility assessment will be considered as complete and the subject will be considered as

enrolled. The primary caregiver of the enrolled subject will be provided access to the COOL mobile app and the recording period will start.

For up to 5 subjects in the study, if the primary caregiver consents for the use of Cocoon Cam they will be provided with the Cocoon Cam kit at screening visit. The primary caregiver will need to complete a training period to verify subject's primary caregiver's ability to properly connect, operate and upload data using the LENA recorders and uploader as well as the Cocoon Cam. As part of the training period, the primary caregiver will do 1-2 hours of recording using the LENA recorder and successfully upload the data into the LENA cloud server through the internet and use the Cocoon Cam for 1 day and able to start using the Cocoon Cam application. Once the study coordinator verifies that the LENA upload is successful and Cocoon Cam set-up is complete, the training and feasibility assessment will be considered as complete and the subject will be considered as enrolled.

Recording period: During the recording period, the subject will be using the LENA recorder and will complete a daily questionnaire at the end of the each day. At the end of 7 days, the site will perform a phone call. The LENA cry and fuss clock generated from the LENA recorder data for the recorded period will be shared with the primary caregiver through the COOL mobile app. After viewing the cry and fuss clock, the primary caregiver will need to complete a questionnaire on the use of LENA recorder and the content of the COOL mobile app. The primary caregiver will continue using the LENA recorder for the next 7 days. At the end of 14 days, the LENA cry and fuss data for the recorded period will be shared with the primary caregiver and the primary caregiver will need to complete another questionnaire on the use and relevance of the cry and fuss clock and overall relevance of the COOL mobile app. If the primary caregiver consents for the use of Fitbit, the primary caregiver will be provided a Fitbit to record their vital parameters like heart rate and sleep through the 14 days after enrolment.

For the primary caregiver who consented for the use of Cocoon Cam will use the Cocoon Cam and would need to record the cry and sleep start and end time through the COOL app around the clock. In addition, the primary caregiver will need to complete a questionnaire on the usability of the Cocoon Cam.

End of study: At the end of the recording period, the primary caregiver will schedule an appointment with the PI. At the end of study visit, the primary caregiver will discuss the data provided by the LENA recorder and the COOL mobile app with the PI and PI will use the data to explain to the primary care giver if there is any specific crying pattern based on the objective data from LENA. The Primary caregiver and PI will complete a questionnaire each on the use of the data provided by the LENA recorder during their discussion.

For the primary caregiver who consented for the use of Cocoon Cam, the primary caregiver and HCP will need to complete a questionnaire on the usability of the Cocoon Cam.

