10 STATISTICS

10.1 Sample size calculation

Because of the exploratory nature of this study, no formal sample size calculation will be performed. This study plans to have 20 completed subjects. Considering a 20% drop-out rate, approximately 25 subjects are planned to be enrolled.

Assuming a standard deviation of 1.25 for the primary rating score, 20 subjects will achieve a half-width of at most 0.70 for the two-sided 95% confidence interval with a conditional probability of 0.90.

The overall probability of achieving this precision in capturing the true mean is the product of the half-width probability and the confidence level, which is 0.855.

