11.4 Recruitment and Informed Consent

Parents/Guardians of potentially eligible participants will be informed about the study and what is expected in case of participation to the study. Information on the study is incorporated in the Informed Consent Form. The parent/guardian must be given as much time as needed to read and understand the Informed Consent Form, to ask questions, and to reach a decision, including time for consultation with family members or others. Adequate time and resources must be provided for informed-consent procedures.

If the parent/guardian is willing that his/her child will participate, he/she will be asked to sign the Informed Consent Form. The Investigator or delegate carrying out the procedure will co-sign and date the Informed Consent Form. The parent/guardian has the right to make a request to withdraw his/her child from the study at any time, without giving any reason, without patient's medical care or legal rights being affected.

The main consent will include:

- Participation in the COOL study, agreement on all analyses of data as per protocol
- Use of personal information in encoded form within the scope of the research as defined in the Protocol (including e.g. future post-hoc analyses)
- Transfer of encoded personal data outside of the SG

If the parent/guardian of the subject does not agree with one of the above, he/she cannot participate in the study.

Additional consent will include:

- Use of personal information in encoded form for future research out of scope of study purposes, i.e. research related to broader scope of Early Life Nutrition
- Contacting the subject in the future for follow-up studies
- Consent for the use of Fitbit and analyse the data generated from Fitbit for primary caregiver
- Consent for the use of Cocoon Cam

If the parent/guardian of the subject does not agree with one of the above, he/she can participate in the study

In case, the primary caregiver of the infant is not the parent who signed informed consent, then a separate informed consent will be signed by the primary caregiver to consent to use the Fitbit during the study.

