3 PROTOCOL DEVIATIONS

All protocol deviations will be discussed prior to Database Lock. Possible deviations for this study are:

Description of Deviation	Deviation Type
Visit window deviation	Minor
Not all questionnaires completed	Minor
Enrolled with Cocoon Cam but failed to use Cocoon Cam during the study period	Minor

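### Enrolment of camera families hinges on setting up an optional camera, with no stated LENA-only fallback, so set-up failures are missing from the camera usability ratings

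*Protocol*

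**What the plan says.** **Without the camera.** Protocol 3.2 and 6.1 treat training as finished, and the subject as enrolled, once the coordinator has confirmed the LENA upload.

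**With the camera.** Section 6.1 opens this cohort with "For up to 5 subjects in the study, if the primary caregiver consents for the use of Cocoon Cam". Training then adds a day of camera use and being able to start its app. Enrolment follows on a double condition: "Once the study coordinator verifies that the LENA upload is successful and Cocoon Cam set-up is complete". The synopsis and 3.2 carry the same rule.

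**Failing the training.** The screening paragraph of 6.1 says of a caregiver "unable to perform all of the technical prerequisites (after troubleshooting assistance is provided), they will not be able to take part in the trial", and calls this a screen failure. Section 7.4 includes the camera among the items that a screen failure returns after training.

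**Status of the camera.** Section 11.4 lists it under additional consent and adds: "If the parent/guardian of the subject does not agree with one of the above, he/she can participate in the study". After enrolment, SAP 3 grades this as a minor deviation: "Enrolled with Cocoon Cam but failed to use Cocoon Cam during the study period".

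**Ratings.** Caregivers rate camera usability at Day 7, Day 14 and the end of the study, and the HCP at the end of the study (Protocol 6.1 and 6.3.8). All of these come after enrolment. Both analysis sets in SAP 4.1 consist of enrolled subjects. SAP 4.2 reports screen failures as a number and percentage in the flow diagram, with no stated breakdown by cause.

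**The concern.** The primary outcome rates the LENA cry and fuss clock and the COOL app. The camera plays no part in it, so failing to set up the camera is no reason to leave a family out of the main study. As the text stands, accepting an optional extra can cost a family its place, although refusing that extra cannot.

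The more important consequence is for the camera itself. One exploratory objective is how usable caregivers find it. A caregiver defeated by set-up has had the worst possible usability experience, yet never reaches a camera questionnaire. Table 6.3 would then summarise only those for whom set-up worked, and the failures would be visible only inside a single screen-failure count. In a proof-of-concept study of usability, the proportion who cannot get a device working is a result in its own right.

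**Working it through.** **1. The plan's own figures.** Protocol 10.1 states: "Assuming a standard deviation of 1.25 for the primary rating score, 20 subjects will achieve a half-width of at most 0.70". The interval is two-sided at the 95% level, and the plan attaches a probability of 0.90 to reaching this width. With n = 20, SD = 1.25, h = 0.70 and a t-based interval, P(half-width ≤ h) = P(χ² on n − 1 df ≤ h²·n·(n − 1)/(t²·SD²)). With t = 2.093 the bound is 0.49 × 20 × 19/(4.381 × 1.5625) = 27.2, and the probability on 19 df is 0.900. Conditional on the interval covering the mean, it is 0.896, and the joint probability is 0.851 against the stated 0.855. The plan's figures are reproduced closely enough for this purpose.

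On enrolment: "Considering a 20% drop-out rate, approximately 25 subjects are planned to be enrolled". This is 20/(1 − 0.20) = 25, which agrees.

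**2. Does the camera rule disturb these targets?** The 25 are enrolled subjects, and enrolment comes after training. A family that fails camera set-up was never among the 25. If recruitment continues, 25 enrolled and 20 completers stand. Only if failures were taken out of the 25 and not made good would expected completers fall, to (25 − k) × 0.80:

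- k = 1 gives 19.2; k = 5, the extreme, gives 16.0.
- The conditional probability of a half-width of at most 0.70 is 0.848 at n = 19 and 0.641 at n = 16.

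The protocol does not describe that situation.

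**3. The rules side by side, for families whose LENA upload works.**

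| Family | Outcome as written |
|---|---|
| Declines the camera (11.4) | Can take part |
| Sets the camera up, then never uses it (SAP 3) | Enrolled, minor deviation |
| Accepts the camera, set-up fails (6.1) | Condition for enrolment not met; no fallback stated |

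**4. How many families.** The documents give no set-up failure rate, so f is assumed. With 5 cameras issued, the expected number of failures is 5f: 5 × 0.10 = 0.5 and 5 × 0.40 = 2. The chance of at least one is 1 − (1 − f)⁵:

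- f = 10%: 1 − 0.90⁵ = 0.41
- f = 20%: 1 − 0.80⁵ = 0.67
- f = 40%: 1 − 0.60⁵ = 0.92

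**5. Effect on a camera rating (illustration).** The documents do not give the scale of the camera items, so assume 0 to 5, as for the primary ratings. Suppose 4 of 5 families succeed and rate 4, and the fifth would have rated between 0 and 2. The reported mean is 4.0. The mean over all who tried would be (4 × 4 + 0)/5 = 3.2 to (4 × 4 + 2)/5 = 3.6. One missing family moves the summary by 0.4 to 0.8 points.

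**The case against.** The strongest reply is that no sentence expressly dismisses a family for a camera failure. The screen-failure sentence stands in the LENA paragraph of 6.1, before the camera is introduced there, and its list of returns omits the camera. The camera paragraph has no dismissal sentence. Section 7.4 says what a screen failure hands back, not what makes one; a camera family that failed the LENA upload would return the camera too. Nor does anything forbid a caregiver from withdrawing the camera consent and enrolling on LENA alone. All of this stands. What remains is that the camera paragraph states both conditions for enrolment, 6.1 speaks of all technical prerequisites, and no LENA-only route is written down. A site following the text would not enrol the family.

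A reader might also infer that these families are lost from the primary analysis. The documents do not support that, because enrolment is counted after training and recruitment can continue to target.

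It can further be said that consent, training and deviation grading belong to different stages, so the three rules are not in formal contradiction. That is fair; the difficulty is that their joint effect has no stated rationale.

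Finally, the plan allows camera families up to seven days of screening rather than two, every family already passes a LENA technical check, camera usability is exploratory, SAP 5.2.5 makes analysis of Cocoon Cam data post hoc, and no hypothesis is tested. These points limit the consequences. They do not recover the missing set-up failures.

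**Conclusion.** The point holds as a question of avoidable selection, not of sample size. Followed as written, the enrolment rule keeps out a LENA-capable family whose camera set-up fails, although declining or later ignoring the camera excludes nobody. That wastes recruitment and adds a little device-skill selection. It also probably biases the camera usability summary upward.

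The size is unknown. The figure of 0.5 to 2 of 5 camera families rests on an assumed failure rate of 10% to 40% and on five cameras being issued. The direction of the bias rests on the reasonable but undocumented premise that those who fail set-up would rate the camera lower. Any effect on the primary ratings is confined to the few families offered a camera and cannot be quantified from the documents. The main gain from a change is in an exploratory result for at most 5 enrolled families. It is still worth making, because it is cheap and a single missing rating carries much weight among five.

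**What to change.** - **Protocol synopsis, 3.2 and 6.1:** make enrolment depend on the LENA upload alone for every subject. State that a family whose camera set-up fails after troubleshooting continues in the LENA-only cohort.
- **Protocol 7.4, and the screen-failure sentence in 6.1:** align both with this rule, so that it is clear which failure makes a screen failure and what a family returns if only the camera fails.
- **SAP, beside Table 6.3:** report the number failing camera set-up out of the number issued a camera. This is needed even after the protocol change, because a family continuing on LENA alone would still give no rating of camera use.
- **SAP Fig 1:** split screen failures by cause (LENA technical failure, camera technical failure, other). The camera category would be empty under the new rule, but is needed for any family screened under the present one.

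The cost is a sentence in three protocol places, two alignments and two SAP lines, with no extra visits or staff. The downside is small: fewer than 5 enrolled subjects may end up with camera data.
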